#### Interactions with Subgroups

In this study, bridging therapy is prespecified as a covariate in the subgroup analysis. The RR values and 95% confidence intervals of the incidence of the trial and control groups in each subgroup are calculated respectively. Summary tables will be produced for the predefined subgroups and interactions between treatment and these subgroups will be investigated, using a logistic regression model. A separate model will be used for each interaction to determine its significance.

#### Secondary Efficacy Analyses

#### The proportion of patients with an mRS score of 0-2 at 90±7 days

The proportion of patients with 90-day mRS score of 0-2 in treatment groups will be compared by Chi-squared tests. This will also be tested by logistic regression model. The odds ratio with 95% CI will be reported.

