#### 3.4 Measures to control bias

#### 3.4.1 Randomization

The central randomization method is adopted in this study, and the central randomization system is used to set dynamic block randomization. The proportion of subjects in the treatment group and the control group is 1:1 in each center, and each center assigned random number to each enrolled subject in the way of competitive enrollment.

After the subjects complete all screening tests and the investigators determine that they meet the inclusion criteria or do not meet the exclusion criteria, the staff of the research center is responsible for entering the basic information of the patients (initials, age, sex, identification code, etc.) into the central randomization system based on the network. The system will automatically generate a random number and subject ID according to the above principles and feed back to the central investigator via the network whether the patient is assigned to the trial group (rhTNK-tPA 0.25mg/kg group) or the control group (rT-PA 0.9mg/kg group). Investigators at the research center received the results of randomization and then treated the patients according to the appropriate group.

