#### Multicenter Studies

In multicenter randomized controlled clinical study, there were some differences affect in different center due to different baseline, clinical practice or other factor, therefore, center effect analysis was required. Analysis will be performed to exclude the center effect.

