#### Main Model

The proportion of patients with 90-day mRS score of 0-1 between treatment groups will be

compared by Cochran-Mantel-Haenszel Chi-squared tests with the adjustment of center effect. Effect rate with 95% CI in each treatment group and the RR or RD of effect rates between the two groups and corresponding 95% CI will be reported. This will also be tested by logistic regression model with the adjustment of center effect and mRS scores at baseline. The odds ratio with 95% CI will be reported. According to the protocol, superiority of the treatment group will be tested if the non-inferiority is met.

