#### MRS level distribution at 90±7 days (Shift Analysis /Ordinal Distribution)

Differences in mRS level distribution at 90 days between the two treatment groups will be tested by Wilcoxon rank sum test. This will also be tested by ordinal logistic regression model. The common odds ratio with 95% CI will be reported.

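### Randomisation is balanced 1:1 within center, but only the primary endpoint gets a center-stratified test; the tests named for the secondary efficacy endpoints are unstratified and their models' covariates are not listed

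*Supplement*

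**What the plan says.** **Randomisation.** Protocol V2.2, section 3.4.1, states that "the central randomization system is used to set dynamic block randomization" and that "The proportion of subjects in the treatment group and the control group is 1:1 in each center". Center is therefore in effect a randomisation stratum, although the protocol does not use that word.

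**General clauses on center.** Final SAP section 9 (Multicenter Studies) accepts that centers may differ, calls for a center analysis, and ends: "Analysis will be performed to exclude the center effect". It names no endpoint, method or rule for small centers. Protocol 12.2 says that center will be considered for the efficacy endpoints as the situation requires, and protocol 12.4 refers the secondary endpoints back to those principles.

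**Primary endpoint.** SAP section 12 (Main Model) prescribes "Cochran-Mantel-Haenszel Chi-squared tests with the adjustment of center effect", together with a logistic model containing center and baseline mRS.

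**Secondary efficacy endpoints, same section.**
- mRS 0-2: "The proportion of patients with 90-day mRS score of 0-2 in treatment groups will be compared by Chi-squared tests", plus a logistic model.
- mRS shift: differences "will be tested by Wilcoxon rank sum test. This will also be tested by ordinal logistic regression model".
- NIHSS response and Barthel at least 95: chi-squared plus a logistic model.
- EQ-5D: t test or Wilcoxon.

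No center term appears in any of these paragraphs, and the covariates of the models are not given.

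**Safety.** SAP section 13 names chi-squared or Fisher tests, plus a logistic model for bleeding events, again without mention of center.

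**The concern.** When allocation is balanced within center, differences between centers fall equally on both arms. A pooled test still counts that between-center variation in its standard error. It then rejects slightly less often than its nominal 5% under the null and has less power than the design allows.

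The plan is also inconsistent. Section 9 wants the center effect removed, and the primary analysis of the mRS removes it. The analyses of mRS 0-2 and of the full mRS distribution, from the same assessment in the same patients, use tests that do not.

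With model covariates unlisted and center left to discretion in the protocol, two analysts could follow the plan and report different secondary odds ratios. The stakes are the precision and reproducibility of the secondary efficacy results in an open-label trial.

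**Working it through.** **1. Is the sample size touched?** The plan's own figure is 642 per group: one-sided alpha 0.025, power 0.85, control rate 59.32%, RR 1.07, margin 0.937. On the log-RR scale

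n = [(1-pT)/pT + (1-pC)/pC] × (z0.975 + z0.85)² / [ln RR - ln 0.937]².

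With pT = 1.07 × 0.5932 = 0.6347, this is 1.2613 × 8.978 / 0.01762 = 642.8, or 643. A Wald calculation on pT - 0.937 pC gives 641, and the Farrington-Manning score test has power 0.850 at n = 642. The stated figure is reproduced. It rests on the primary endpoint alone, whose test is center-stratified, so nothing here changes it.

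**2. Mechanism.** Let τ be the between-center SD of the log odds and p the event rate. To first order the between-center share of the binomial variance is

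f = [τ p(1-p)]² / [p(1-p)] = τ² p(1-p).

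The pooled test then has actual two-sided size of about 2[1 - Φ(1.96/√(1-f))].

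- p = 0.70, τ = 0.5: f = 0.25 × 0.21 = 0.053; size about 4.4%.
- p = 0.70, τ = 0.75: f = 0.5625 × 0.21 = 0.118; size about 3.7%.
- p = 0.02, τ = 0.5: f = 0.25 × 0.0196 = 0.005; size practically 5%.

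**3. Simulation for mRS 0-2.** N = 1,430, exact 1:1 within center, two-sided 5%, 4,000 runs per cell. Assumptions not in the documents: 50 centers, control rate 70%, odds ratio 1.37.

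| SD (logit) | Type I, chi-squared | Type I, CMH | Power, chi-squared | Power, CMH |
|---|---|---|---|---|
| 0 | 4.95% | 4.95% | 75.8% | 75.8% |
| 0.25 | 4.7% | 4.9% | 74.8% | 75.2% |
| 0.5 | 4.9% | 5.4% | 71.8% | 73.5% |
| 0.75 | 3.9% | 5.1% | 69.4% | 73.1% |
| 1.0 | 3.4% | 5.1% | 64.0% | 69.9% |

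The Monte Carlo standard error of a 5% rate is √(0.05 × 0.95/4000) = 0.34 points, so small departures from 5% should not be read closely.

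**4. Second simulation, other assumptions.** Response about 57%, within-center odds ratio 1.35; 6,000 null and 3,000 alternative runs.

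| Centers | SD | Type I, unadjusted / CMH | Power, unadjusted / CMH | Loss (points) |
|---|---|---|---|---|
| 22 | 0.5 | 4.5% / 5.1% | 74.7% / 76.5% | 1.8 |
| 22 | 0.8 | 4.0% / 5.3% | 69.6% / 73.8% | 4.2 |
| 50 | 0.5 | 4.7% / 5.2% | 74.3% / 76.2% | 1.9 |
| 50 | 0.8 | 4.3% / 5.5% | 68.7% / 73.0% | 4.3 |

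The two sets agree in direction and size.

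**5. Rare safety event.** Rate 2%, odds ratio 2.3, 50 centers, chi-squared against CMH: power 79.8% against 79.7% at SD 0.5, and 87.8% against 88.5% at SD 1.0. The difference is under one point, as step 2 predicts.

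**6. Odds ratios.** In the 57% setting at SD 0.5 the unadjusted odds ratio averages 1.33 and the center-stratified one 1.35. The standard error of the log odds ratio is 0.109-0.110 unadjusted and 0.112-0.113 stratified. Stratifying moves the estimate to the within-center effect and slightly widens its interval.

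**The case against.** The best reply is that the SAP is not silent. Section 9 is not limited to the primary endpoint, the protocol allows center adjustment for efficacy endpoints, and an unlisted covariate is not an excluded one. This stands as far as the logistic and ordinal models go: a reader might infer that every secondary and safety comparison ignores center, and the documents do not support so firm a statement. It does not rescue the named tests. A plain chi-squared or rank-sum test is unstratified, and a clause without a method does not turn it into CMH or van Elteren.

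Two further inferences are tempting and fail:
- **That the secondary intervals are too wide.** This is not so for the odds ratios that the SAP reports. Step 6 shows that stratifying slightly enlarges their standard error. The marginal and within-center odds ratios are different quantities, and the gap is small.
- **That safety results lean towards no difference.** For rare events the loss is negligible, and center strata would be sparse or empty, so an unstratified Fisher or chi-squared test is defensible.

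It is also true that any error is conservative, that the trial is not sized on the secondary endpoints, and that simple tests are a legitimate choice. These facts limit the importance of the point. They do not remove the inconsistency.

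**Conclusion.** The point holds as a minor one. The named secondary efficacy tests do not follow the randomisation or the SAP's own statement on center effects, and the model covariates are left open. For common efficacy endpoints the cost is about 0 to 2 power points up to a between-center SD of 0.5, and about 4 points at 0.75 to 0.8. With no variation between centers it is zero.

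These sizes depend on assumed SDs, center numbers (22 and 50), event rates and effects; the documents give no between-center variance. The direction does not depend on them: with balance within center, ignoring center makes the test conservative and creates no false-positive risk. The primary non-inferiority result, the superiority test that follows it and the sample size are untouched.

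**What to change.** In SAP section 12:
- Use CMH by center for mRS 0-2, NIHSS response and Barthel at least 95.
- Use the van Elteren test (Wilcoxon stratified by center) for the mRS shift, with an ordinal model that includes center.
- Include center in the EQ-5D comparison.
- List the covariates of every logistic and ordinal model, and note that center-adjusted odds ratios are within-center effects.

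In section 9, name the endpoints to which the center clause applies, and give a rule for pooling very small centers that is fixed before unblinding. In section 13, state that rare safety events such as sICH and PH2 keep unstratified chi-squared or Fisher tests.

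The cost is SAP wording and a few lines of SAS, with no new data. The small downside is that a pooling rule has to be written and followed.

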#### MRS level distribution at 90±7 days (Shift Analysis /Ordinal Distribution)

Differences in mRS level distribution at 90 days between the two treatment groups will be tested by Wilcoxon rank sum test. This will also be tested by ordinal logistic regression model. The common odds ratio with 95% CI will be reported.

### The proportion of patients whose NIHSS score is 0-1 or is improved compared to the baseline with $\Delta$ NIHSS $\geq$ 4 at 24±2h, 7±1d or before discharge (whichever comes first)

The proportion of patients whose NIHSS score is 0-1 or is improved compared to the baseline with  $\Delta$ NIHSS  $\geq$  4 at 24  $\pm$  2h, 7  $\pm$  1d or before discharge (whichever comes first) in treatment groups will be compared by Chi-squared tests. This will also be tested by logistic regression model. The odds ratio with 95% CI will be reported.

#### Health-related quality of life (EQ-5D) at 90±7 day

Health related quality of life will be measured using EuroQol EQ-5D scale among the survivors. Treatment differences will be tested using student t-test or Wilcoxon rank sum test as appropriate. The difference of the scores between two groups with 95% CI will be reported.

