#### 1.3 Overview of clinical studies at home and abroad

#### (1) NOR - TEST trial [23]

The purpose of the NOR-test was to compare the safety and efficacy of intravenous thrombolysis with tenecteplase and alteplase. NOR - TEST Trial for phase III, multicenter (13) research center, prospective, randomized, open label, end blinded clinical trial, the target population in super acute phase of ischemic stroke (< 4.5 h) patients or symptoms occur within 4.5 h after waking, suspected of acute ischemic stroke and suitable for thrombolysis or thrombectomy bridge before the treatment, according to the proportion of 1:1 randomly given intravenous injection of tenecteplase at 0.4 mg/kg (maximum 40 mg) or alteplase at 0.9 mg/kg (maximum 90 mg). The primary endpoint was the ratio of good prognosis at 90 days (mRS 0 to 1). A total of 1107 patients were enrolled in the study, 7 patients dropped out of the trial, and 1100 patients were randomly assigned to the tenecteplase group (n=549) or alteplase group (n=551). The median age was 77 years (64-79), and the median NIHSS score was 4 (2-8). A final diagnosis of non-ischemic stroke or non-TIA was

found in 99 (18%) patients in the tenecteplase group and 91 (17%) patients in the alteplase group. A total of 354 patients (64%) in the tenecteplase group and 345 patients (63%) in the alteplase group were included in the final outcome analysis.

The results showed as follows: ① The incidence of primary endpoints in the two groups was 64% and 63%(OR 1.08, 95%CI 0.84 to 1.38;P = 0.52);② The 90-day mortality rates were 5% and 5%(P = 0.68), respectively.(3) The incidence of serious adverse events was similar in both groups (26%).

Conclusion: Tenecteplase is not superior to alteplase, and the safety of both is similar. However, in general, the majority of patients in this study were patients with mild stroke, and about 75% of the patients had NIHSS\(\leq\)7 points before treatment, and the proportion of patients with great artery occlusion was small. The research on patients with severe stroke still needs to be continued.

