#### 10. Data handling conventions

#### Premature Withdrawal and Missing Data

If any subject withdraws prematurely from the study (prior to the final visit D90±7 days assessment), they are required to complete the withdrawal visit in the CRF. The reasons for withdrawal will be presented in a summary table. For the purposes of summaries and analysis of clinic visit data, this visit will be assigned to the next scheduled clinic visit for that patient, regardless of whether the date falls within the next visit window.

Patients who withdraw before the end of the study, but who do provide at least one post-baseline measure for a particular endpoint, will be included in the analysis.

Patients who do not attend any visits after randomization will be excluded from analysis of efficacy outcomes and safety outcomes, as no post-baseline data will be available.

Missing data will not be imputed in the main analysis. Illogic data needs to be investigated by the data management facility, investigators or Sponsor together to identify possible reasons, and restrained by the parties in a data review meeting after full discussion: illogic data, if sufficient reasons have been found to indicate its incorrectness, should be removed, or otherwise, should be remained and subjected to analysis and the results obtained without such removed data should be treated as sensitivity analysis; If there is data collected in the study that is not in accordance with the program requirements such as planned external visits, it will be presented in a list, and descriptive or comparative analysis will be decided at the data review meeting depending on the specific situation of the data. In sensitivity analysis, multiple imputation was performed to impute the missing data of the primary efficacy outcome.

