#### The proportion of patients with a Bathel score ≥ 95 points at 90±7 days

The proportion of patients with a Bathel score ≥ 95 points at 90 days in treatment groups will be compared by Chi-squared tests. This will also be tested by logistic regression model. The odds

ratio with 95% CI will be reported.

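### EQ-5D is compared in survivors only with no supporting analysis that includes deaths, and the SAP does not say how deaths count for Barthel ≥95 or, for early deaths, NIHSS response

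*Supplement*

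**What the plan says.** **EQ-5D.** Final SAP, section 12: "Health related quality of life will be measured using EuroQol EQ-5D scale among the survivors". The next sentence gives the test: "Treatment differences will be tested using student t-test or Wilcoxon rank sum test as appropriate". No value or rank is assigned to a patient who has died.

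**Barthel.** Final SAP, section 12: "The proportion of patients with a Bathel score ≥ 95 points at 90 days in treatment groups will be compared by Chi-squared tests". A logistic regression follows. Neither a denominator nor a rule for deaths is stated. In protocol V2.2 (flow chart and section 7.4.4) Barthel and EQ-5D are collected at the day-90 visit only.

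**NIHSS response.** This is read early, at 24 h, day 7 or before discharge (final SAP, sections 3 and 12). Protocol sections 7.4.1 and 7.4.3 schedule NIHSS at 24 h and at day 7 or discharge.

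**Missing data.** Final SAP, section 10: "Missing data will not be imputed in the main analysis". The only imputation is for the primary outcome: "In sensitivity analysis, multiple imputation was performed to impute the missing data of the primary efficacy outcome". Patients who withdraw early, but "who do provide at least one post-baseline measure for a particular endpoint, will be included in the analysis". Also: "Patients who do not attend any visits after randomization will be excluded from analysis of efficacy outcomes and safety outcomes".

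**Where death is already counted.** Grade 6 of the mRS is death (protocol Annex 3), and 90-day mortality is a separate safety endpoint (final SAP, sections 3 and 13).

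**The concern.** Being alive at day 90 is a result of the treatment period, not a baseline characteristic. Once the comparison is restricted to survivors, the two groups are no longer those that were randomized. If one arm loses more of its sickest patients, its remaining patients can look the same or better. The same happens to a responder proportion if deaths leave the denominator instead of counting as failures.

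In an open-label non-inferiority trial, secondary endpoints are read as support for the claim that the new drug is no worse. A quality-of-life comparison that cannot register excess deaths supports that claim less than it appears to.

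**Working it through.** **1. Which endpoints have a value for a patient who dies?**

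| Endpoint | When measured | Value for a death | What the SAP says about deaths |
|---|---|---|---|
| mRS 0–1, mRS 0–2, mRS shift | day 90 | yes, grade 6 | nothing further needed |
| EQ-5D | day 90 | none | excluded, explicitly |
| Barthel ≥95 | day 90 | none | silent |
| NIHSS response | 24 h, day 7 or discharge | none if death precedes the reading; otherwise observed | silent |

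For EQ-5D the exclusion is written down. For Barthel it is an inference: the only measurement is at day 90, nothing is imputed, and the section 10 rule asks for a post-baseline value of that endpoint. A logistic regression also omits any patient without a value unless a rule supplies one. For NIHSS the same reasoning reaches only deaths before the reading used. Deaths between that reading and day 90 keep their NIHSS value.

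**2. Number of deaths.** The plan gives no figure of its own on this point. The group size is 715 (final SAP, section 6). Its base of 642 reproduces with a score-type calculation at a risk ratio of 1.07, one-sided α 0.025, power 0.85 and margin 0.937; 642/0.9 = 713.3, close to the stated 715. Protocol 1.3 cites 90-day mortality of 5% in both arms of a phase 3 tenecteplase–alteplase trial, and 7.7% on alteplase in an alteplase–placebo trial.

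- 715 × 0.05 ≈ 36 deaths per arm
- 715 × 0.077 ≈ 55 deaths per arm

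These are 90-day deaths. They apply to EQ-5D and Barthel, not to the early NIHSS endpoint, for which the documents give no death figure.

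**3. Effect on Barthel.** Let s be the rate of Barthel ≥95 among survivors and m the mortality. With deaths as failures the rate is s × (1 − m). Assumptions, not in the documents: s is equal in both arms at 60% or 70%, and mortality is 5% in one arm and 7.7% in the other.

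| s | Rate at m = 5% | Rate at m = 7.7% | Difference | Survivors-only RR |
|---|---|---|---|---|
| 60% | 0.60 × 0.95 = 57.0% | 0.60 × 0.923 = 55.4% | 1.6 points | 1.00 |
| 70% | 0.70 × 0.95 = 66.5% | 0.70 × 0.923 = 64.6% | 1.9 points | 1.00 |

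The risk ratio with deaths as failures is 0.923/0.95 = 0.97 or 0.95/0.923 = 1.03, depending on which arm has more deaths. With equal mortality the factor (1 − m) cancels and the ratio is 1.00 either way; only the level moves.

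**4. Effect on EQ-5D.** Assume a survivor mean index of 0.80 in both arms, death valued at 0, and the same mortality split. Survivors only, the difference is 0. With deaths included it is 0.80 × (0.95 − 0.923) = 0.022.

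**5. Scale.** For a proportion near 60% with 715 per arm, the 95% confidence half-width for a difference is 1.96 × √(2 × 0.6 × 0.4/715) ≈ 0.051, about 5 points. The 1.6–1.9 points in step 3 lie well inside it.

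**The case against.** The strongest reply is that deaths are not hidden from the trial. They enter the primary endpoint, mRS 0–2 and the shift analysis, and mortality has its own comparison. The secondary endpoints carry no multiplicity-controlled claim. This stands, and it limits the consequence. It does not make survivors-only EQ-5D a randomized comparison.

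On Barthel, counting a death as not having reached 95 needs no imputation. The SAP's written denominators, for the primary endpoint (section 3) and for event rates (section 10), are all patients enrolled in the group. This also stands in part: the fault is silence, not a stated rule that removes deaths. Neither denominator is written for Barthel, so the silence still has to be filled.

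A reader might infer that three secondary endpoints all discard the worst outcomes. The documents establish that for EQ-5D, make it plausible for Barthel, and confine it to early deaths for NIHSS. Those early deaths are not irrelevant: protocol section 9.7 places most symptomatic intracranial hemorrhages within 24 hours and notes rapid death in some cases.

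A reader might also infer that these endpoints would contradict the mRS result. Nothing here shows that. The cited tenecteplase–alteplase trial had equal mortality, the unequal split is an assumption, and the resulting differences are small against sampling error.

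Finally, a reader might carry the section 10 exclusion of patients with no visits after randomization over to the mRS. Its stated ground is the absence of post-baseline data, and death is itself an mRS grade, so that does not follow.

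**Conclusion.** The point holds in a limited form. The EQ-5D comparison conditions on a post-randomization outcome and has no companion analysis that includes deaths. That much is explicit. For Barthel ≥95, the day-90-only schedule and the no-imputation rule would, read literally, drop deaths; the SAP should state otherwise if that is not intended. For NIHSS response the gap covers only deaths before the assessment.

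The size is modest and depends on unequal mortality, which is assumed in step 3. If mortality is equal, the Barthel risk ratio is unchanged. The primary endpoint, its sample size and the mRS secondary endpoints do not depend on this point.

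**What to change.** Add to final SAP sections 10 and 12, for the FAS:

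- **Barthel:** a patient who dies before the day-90 assessment counts as Barthel <95 and stays in the denominator, in both the chi-squared test and the logistic model.
- **NIHSS response:** a patient who dies before the assessment used counts as a non-responder.
- **EQ-5D:** add a Wilcoxon comparison with deaths given the worst rank. If a mean difference is also wanted, index 0 for death is one convention and should be named as such. The EQ-5D form anchors 0 on its 0–100 health scale as the worst imaginable health, not death, so ranking is the safer choice. Report the survivors-only result alongside, labelled descriptive.

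These rules concern deaths, where the outcome is known. Patients alive without an assessment stay under the existing no-imputation rule.

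The cost is wording and one extra table, with no new data. The downside is that the EQ-5D distribution gains a spike at its lowest value, so the rank test replaces the t-test for that analysis.
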